9.2.1 Duration of the study

Patients will be encouraged to participate in the registry and followed up to ten years after entry of the first patient or until definitive pump explanation whichever comes first.

9.2.2 Eligibility criteria

9.2.2.1 Inclusion criteria

- Patients with type 1 diabetes treated with Insuman Implantable 400 IU/mL in the MIP at study entry and treated in accordance with the Insuman Implantable Summary of Product Characteristics.
- Patient (or a legal representative) has provided written informed consent to participate in the study.

9.2.2.2 Exclusion criteria

• None

9.2.3 Analysis population(s)

Eligible patients will be patients for whom an informed consent form (ICF) has been signed and should have taken at least one dose of Insuman Implantable 400 IU/mL.

For this longitudinal study, analysis will be done on all eligible patients at baseline (baseline population), and then follow up data analysis will be performed yearly for the ten year duration of the study.

Information will be collected for all patients considered for the study on a tracking log and entered in the study database in order to describe the extent of potential selection bias. This information will be very minimal and non-identifiable since it will be collected outside the patient's consent; and may include: patient's age range, gender and reason for non-inclusion (patient consent not provided, or other reason).

9.2.4 Modalities of recruitment

9.2.4.1 Investigator selection

All physicians who are trained and who may prescribe Insuman Implantable 400 IU/mL at the certified sites in participating European Union (EU) countries are eligible for enrolling their patients into the Registry and will be encouraged to do so. Information on the PASS will be part of the training for certification. There is no selection quota or randomization for the investigators. All country specific regions are treated equally.

Non-Interventional Post Authorization Safety Study (PASS) Amended Protocol 2 20 HUBIN-C-06380 - insulin human Ve

9.2.4.2 Patient selection

The registry will include all patients treated with Insuman Implantable 400 IU/mL using the MIP post launch who agree to participate.

The prescription of therapies is solely the responsibility of the patient's investigator.

All patients who agree to participate in the study will be consecutively enrolled. The patients are those for whom the investigator has decided to prescribe Insuman Implantable 400 IU/mL independent from participation in the registry.

The investigator should refer to the Summary of Product Characteristics, SmPC, and pump manuals for any information on treatment prescribed.

9.3 VARIABLES

Analysis variables include safety variables: important identified risks, important potential risks, and missing information and all AE/SAEs reported.

Main Safety Evaluation criteria (see Section 9.3.1), and other AEs and deaths will be sought from investigators, medical records, death certificates, autopsy, and other sources as available and relevant to the event of interest and will be used to classify metabolic endpoints and pump pocket infections, abnormal healing and skin erosion. All these events will be recorded in the e-CRF, according to the procedures, described in Section 11.

9.3.1 Main Safety Criteria Definitions and Measures

9.3.1.1 Metabolic events

1. Severe hypoglycaemia defined as "An event requiring assistance of another person to actively administer carbohydrate, glucagons, or other resuscitative actions. These episodes may be associated with sufficient neuroglycopenia to induce seizure or coma. Plasma glucose measurements may not be available during such an event, but neurological recovery attributable to the restoration of plasma glucose to normal is considered sufficient evidence that the event was induced by a low plasma glucose concentration" (according to the EMA Guideline CPMP/EWP/1080/00 Rev.1, (5).

A severe hypoglycaemia may also fulfill criteria for SAE (hospitalization, coma, seizure).

- 2. Hyperglycaemia (caused by insulin under delivery due to pump jamming, pump dysfunction or catheter occlusion):
 - Any episode of hyperglycaemia with no apparent medical, dietary or insulin dosage reason will need investigation to identify the origin of the blood glucose (BG) increase. The origin of hyperglycaemia (pump jamming, pump dysfunction or catheter occlusion) will be recorded, as well as the corrective actions taken.
 - Can be associated with ketonemia > 0.5mmoL/L.

Non-Interventional Post Authorization Safety Study (PASS) Amended Protocol 220-Feb-2018HUBIN-C-06380 - insulin humanVersion number: 1

 Or with diabetic ketoacidosis (DKA). Diabetic ketoacidosis, defined as hyperglycaemia with symptoms such as polydipsia, polyphagia, polyuria, nausea, or vomiting; and presence of serum ketones, or moderate or large urinary ketones, will be confirmed with either arterial blood pH <7.25 or serum bicarbonate <15 meq/L; and treatment provided within a health-care facility. DKA is to be reported as an SAE.

9.3.1.2 Pump pocket infection

Surgical interventions for pump implantation or catheter replacement as well as repeated transcutaneous punctures of the pump-pocket for insulin refills and investigation procedures on the implanted system can lead to an infection at the implantation site. This may be treated with antibiotics alone or include pump explantation. When hospitalization is required for pump explantation as part of the treatment, SAE must be reported.

9.3.1.3 Abnormal healing

Patients may experience abnormal healing from the device implantation procedure without developing a pump pocket infection. When hospitalization is required for pump explantation as part of the treatment, SAE must be reported.

9.3.1.4 Skin Erosion

In extreme cases, an implanted device may erode through the skin, resulting in infection of the implant site and pump explanation. When hospitalization is required for pump explanation as part of the treatment, SAE must be reported.

9.3.2 Secondary Safety Criteria Definitions and Measures

9.3.2.1 Hypersensitivity reactions to Insuman Implantable 400 IU/ml or to pump material

Hypersensitivity reactions are all allergic or inflammatory systemic reactions occurring after drug exposure. This may occur in response to the insulin. It can be immediate (within few minutes) or delayed (usually within hours) reactions. The investigator will have to determine if the reaction occurred in response to Insuman Implantable or a pump component. The event is to be reported as an SAE if it meets seriousness criteria (see Section 11).

9.3.2.2 Focal Hepatic Steatosis

Focal hepatic steatosis may occur when the catheter is close to the liver capsule. Cases of focal hepatic steatosis may be associated with catheter obstruction, so cases of catheter obstruction will be reviewed by the investigator who will be requested to provide procedure records for this assessment.

9.3.2.3 Pregnancy and lactation

All cases of pregnancy will be reported. In addition to any AE/SAE related to maternal health during the pregnancy, information will be provided on the fetal outcomes. All cases of lactating women will also be reported. Narratives will be provided on all pregnancies.

9.3.2.4 Other Adverse events

All other AEs will be reported, in particular, complications linked to phenol irritation will be reported as well as potential clastogenic effect of phenol and insulin mitogenic compound.

9.4 DATA SOURCES

Data will be recorded from the patients' own diary and history reviewed by the investigator at the certified sites approximately every 40 to 45 days at the time of routinely scheduled insulin refill visits and/or at ad hoc visits related to complications as is the accepted real world clinical practice for CIPII. The data will be entered into the e-CRF at least every six months. AE and SAE reporting will be expedited on an ongoing basis (see Section 11).

Investigators will collect and provide pre-specified data on study participants at baseline. Data elements provided by investigators and staff will be collected from information routinely recorded in the medical record, or will be prospectively recorded for the purposes of the study. No visits or examinations, laboratory tests or procedures are part of this study.

Scheduled assessments for the study are presented in Section 9.6 Data Management.

9.5 STUDY SIZE

9.5.1 Determination of sample size

This is a descriptive study that is not testing a hypothesis and is including all patients who wish to participate. As such, a formal sample size calculation is not performed. The projected study sample size will be approximately 260 patients.

9.5.2 Sample size

It is planned to recruit all patients who are willing to participate, from all certified investigators in certified centers in all participating EU countries, and without a minimum required for any country or region.

9.6 DATA MANAGEMENT

The investigator or qualified designee is responsible for recording and verifying the accuracy of subject data. All data required by the protocol will be entered via a secure web-based Electronic Data Capture (EDC) System designed for the study. Designated investigator staff will enter the

data required by the protocol into the EDC System of the study. Designated investigator staff will be given access to the EDC System after completion of the relevant training.

Sites will be given the option of completing the paper SAE and paper AE forms for expedited reporting in case they are temporarily unable to access to the EDC system (see Section 11.1.3.2). Paper AE/SAE forms will be shipped to the contract research organization (CRO) for expedited reporting to the MAH. As soon as the sites are again able to access the EDC system, the investigator or qualified designee, is responsible for entering the data temporarily reported on paper AE/SAE forms into the e-CRF.

A data management plan will be created before data collection begins and will describe all functions, processes, and specifications for data collection, cleaning and validation. The e-CRFs will include programmable edits to obtain immediate feedback if data are missing, out of range, illogical or potentially erroneous. Concurrent manual data review will be performed based on parameters dictated by the plan. Ad hoc queries will be generated within the EDC system and followed up for resolution.

High data quality standards will be maintained and processes and procedures used to repeatedly ensure that the data are as clean and accurate as possible when presented for analysis. Data quality will be enhanced through a series of programmed data quality checks that automatically detect out-of-range or anomalous data.

9.6.1 Data collection schedule

The visits will be done according to routine clinical practice for CIPII, which includes routine visits approximately every 40 to 45 days and ad hoc visits for device interventions or BG control. The participating investigator will be asked to record all new patient data including patients new to the study but who may already be on CIPII at entry into the registry. After this initial data entry, sites will collect safety clinical data (AE/SAE) after each contact with the patient (routine scheduled visits every 40 to 45 days or at ad hoc visits). At three and six months after study entry, then every six months (corresponding approximately to the period for four refill visits), other patient data will be recorded in the e-CRF. AE/SAE will have expedited reporting. No post study follow up is required.

9.6.2 Data collected

9.6.2.1 Site/Investigators questionnaire

Date of completion of the most recent training/update of investigator and site certification will be collected.

9.6.2.2 Patient/Subject tracking log

A tracking log will be used for non enrolled patients. To comply with data privacy requirement, data collected on the patient tracking log will be fully anonymous (patients # [1,2,...], included: Yes/No, reason for non-inclusion).

9.6.2.3 Patient data

Data collection at the study entry (i.e. for new patients, the study entry visit should be performed as far as possible at the first clinical visit after pump implantation) will include the following:

- Patients training for pump use assessment,
- Date of signature of the ICF,
- Patient demography: date of birth, sex, weight, and height,
- Insulin history:
 - date of first insulin prescription (duration of type 1 diabetes),
 - indication for IP treatment,
 - initial date of IP treatment,
 - initial date of Insuman Implantable commercial treatment.
- Medical history:
 - Related to the pump use (including occurrence of DKA, hyperglycaemia and severe hypoglycaemia in the year prior to entry into registry or since pump implantation for new patients),
 - Comorbidities:
 - a) hypertension,
 - b) hyperlipidemia,
 - c) cardiovascular diseases.
 - History of diabetes complications (if any):
 - a) active proliferative retinopathy,
 - b) nephropathy,
 - c) neuropathy,
 - d) hypoglycaemic unawareness.
- Concomitant medications will include all medications at this study entry visit.
- Most recent serum glycosylated hemoglobin (HbA1c) value available (and laboratory normal range), with sampling date (No laboratory test is to be drawn in patients for the purpose of the study and timing of test not related to entry into study).
- Most recent urine microalbumin/creatinine ratio available and laboratory normal range, with sampling date (No laboratory test is to be drawn in patients for the purpose of this study).

After each contact with the patients (refill visits -approximately every 40 to 45 days - ad hoc visits or phone calls)

Non-Interventional Post Authorization Safety Study (PASS) Amended Protocol 2 20-Feb-HUBIN-C-06380 - insulin human Version

- Collections of AEs (in expedited manner see safety Section 11), including:
- Severe hypoglycaemia,
- Hyperglycaemia caused by insulin under-delivery (due to pump jamming, pump dysfunction or catheter occlusion),
- Pump pocket infection,
- Abnormal healing,
- Skin erosion,
- Hypersensitivity reaction to Insuman or pump material,
- Focal hepatic steatosis,
- Other AEs, including diabetic complications,
- Pregnancy/lactation.

All AEs will be followed until recovery or stabilization or until the end of the follow-up period, whichever comes first.

In addition, at three and six months after study entry, then every six months corresponding approximately to the period for four refill visits, all the following variables and relevant information will be collected since the last visit in the e-CRF:

- Reason for visits (planned and if not planned; metabolic or device problem since the last data collection),
- Concomitant medications, related to comorbidities, complications and diabetes treatment,
- Most recent urine microalbumin/creatinine ratio available every six months,
- Most recent HbA1c available every six months,
- Review of proper collection of adverse events over the last six months period as described above,
- Date of last rinsing procedure,
- Corrective actions (including subcutaneous insulin injection) in case of pump jamming, pump dysfunction and/or catheter occlusion occurs.

In case of study discontinuation, the following data will be collected:

- Date of discontinuation
- Reason for Study discontinuation (e.g., voluntary withdrawal, definitive pump explantation, death, lost to follow-up)

9.6.3 Procedure for withdrawal of patients from study follow-up schedule

Participants may withdraw consent and discontinue participation in the study at any time, with no effect on their medical care or access to treatment. If a subject discontinues prior to completing the study follow-up period, any known reason for the discontinuation should be documented in the e-CRF. The participating investigators will make documented efforts (repeated phone calls, emails, contact to relatives, etc) to keep track of the patient, obtain information about the patient's health status and a reason for study withdrawal. Patients who continue on CIPII cannot be lost to follow up and must be followed at a certified center.

Pre-identified potential reasons for patient's withdrawal are: patient's withdrawal of consent, patient's or investigator's decision to stop CIPII and switch to another form of treatment, and death. If the patient is withdrawal from the study, following pump explanation in the context of the pump phase-out process, it will be clearly mentioned in the eCRF.

For patients who choose to stop CIPII, they are followed until any AE or SAE are recovered or stabilized. Once the pump has been discontinued and all AEs recovered or stabilized, no further information needs to be collected and the patient withdraws from the study.

9.6.4 Logistic aspects

9.6.4.1 Site documentation of pump performance

Sites document pump parameters such as refill accuracy and technical problems such as catheter obstructions and pump blockages are recorded in the patient's clinical record at the site on the standardized form provided by Medtronic. This is consistent with clinical practice for an implantable pump. When there is a device issue that correlates with any AE's including hypoglycaemia or hyperglycaemia, then that device issue is recorded in the e-CRF AE page or specific e-CRF pages designed to collect event of severe hypoglycaemia and hyperglycaemia.

9.6.4.2 Source Documents

In most cases, the source documents are contained in the subject's medical record and data collected on the e-CRFs must match the data in the medical records. In some cases, the case report forms (CRFs), or part of the CRF, may also serve as source documents. In these cases, a document should be available at the investigator's site and clearly identify those data that will be recorded in the e-CRF, and for which the e-CRF will stand as the source document. All original source documentation is expected to be stored at the site for the longest possible time required by local applicable regulations. The site will be instructed to notify the Market Authorization Holder (MAH) representative before any destruction of medical records of study participants.

9.6.4.3 File Retention and Archiving

To enable evaluations and/or audits from regulatory authorities or Sanofi, the investigator agrees to keep records, including the identity of all participating subjects, all original signed ICFs, copies of all CRFs, SAE forms, source documents and adequate documentation of relevant

20-Feb-2018 Version number: 1

correspondence (e.g., letters, meeting minutes, telephone calls reports). The records should be retained by the investigator according to local regulations, or as specified in the study contract, whichever is longer.

Each site will receive a study site file at study initiation which contains all documents necessary for the conduct of the study and is updated throughout the study. This file must be available for review audits, or inspections and must be safely archived for at least 5 years after completing participation in the study. Documents to be archived include the subject enrolment log and the signed ICF. In the event that archiving of the file is no longer possible at the site, the site will be instructed to notify Sanofi.

9.7 DATA ANALYSIS

IQVIA will be accountable for the statistical analysis of the study data.

A complete overview of planned analyses and limitations due to sample size reduction will be available in the amended Statistical Analysis Plan (SAP).

Eligible patients will be those who have signed an Inform Consent Form (ICF) and have received at least one dose of Insuman Implantable 400 IU/mL. In this non-comparative cohort study, all data analyses will be purely descriptive and no statistical testing will be performed.

These descriptive analyses will be conducted on the entire study population and specific subpopulations of interest (eg, country).

Summary statistics (mean, standard deviation, median, interquartile range, minimum, and maximum values) will be presented for continuous variables and counts and, if relevant, percentages will be presented for categorical and binary variables.

9.7.1 Primary analysis

Since the primary objective is to monitor the important identified risks (see Section 9.3.1 for primary endpoints definitions, the analysis will be descriptive and the multiplicity control will not be considered.

- For the important identified risks including severe hypoglycaemia, hyperglycaemia due to underdelivery of insulin, pump pocket infections, skin erosion, and abnormal wound healing, the time to first event will be depicted by the Kaplan-Meier methodology. Globally, the total number assessed will be given and the number and percentage of events/censored will be calculated. For each time point (six-month and each year time-points), the number of patients at risk, the number of events and the probability (Kaplan Meier estimates) of an event and its 95% confidence interval (CI) will be given.
- Graphically, the cumulative risk over the entire study using life table approach, as well as the instantaneous risk expressed as the hazard function over time, will be presented according to the time expressed in years and using a kernel smoothing method.

Moreover, a horizontal line will represent the incidence rate calculated, as number of patients with one or more events divided by the number of patients treated.

- For rare events, the incidence rate using time to event approach will be considered: number of patients with the event, total patients years for the event, and incidence rate per 100 patient-years with its 95% CI will be calculated.

For the analyses purposes, all AEs will be recorded in the study safety database and classified according to Medical Dictionary for Regulatory Activities (MedDRA® version 16.1 or later) by system organ class and preferred terms (PTs).

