Expected number of patients: Based on the number of patients already included at the time of the amendment n° 2, approximately 260 implanted patients will be followed in the study.

Variables

Data collection at study entry will include the following:

- Patient demography: date of birth, sex, weight, and height,
- Insulin use history,
- Medical history related to use of the implantable pump (including occurrence of diabetic ketotacidosis (DKA), hyperglycaemia and severe hypoglycaemia in the year prior to entry into the study or since pump implantation for patients recently implanted),
- Comorbidities, and history of diabetes complications,
- Concomitant medications, at entry visit,
- Most recent Urine microalbumine/creatinine ratio available and laboratory normal range, with sampling date (No laboratory test is to be drawn in patients for the purpose of the study),
- Most recent Serum glycosylated hemoglobin (HbA1c) and normal laboratory range with sampling date.

Patient data collected during the follow-up

After each contact with the patients (refill visits occur approximately every 40 to 45 days, *ad hoc* visits or phone calls), the investigator will report adverse events (in an expedited manner), including:

- severe hypoglycaemia,
- hyperglycaemia caused by insulin under-delivery (due to pump jamming, pump dysfunction or catheter occlusion),
- pump pocket infection,
- abnormal healing,
- skin erosion,
- hypersensitivity reaction to Insuman or pump material,
- focal hepatic steatosis,
- other adverse events (AEs), including diabetic complications,
- pregnancy/lactation.

In addition, at three and six months after study entry, then every six months (corresponding approximately to the period for four refill visits) all the following variables and relevant information since the last visit/data collection:

- Reason for visits (planned and if not planned; metabolic or device problem since the last collection),
- Concomitant medications, related to comorbidities, complications and diabetes treatment,
- Most recent urine microalbumin/creatinine ratio available every six months,

- Most recent HbA1c available every six months,
- Check of AE reporting.

In case of study discontinuation, the following data will be collected:

- Date of discontinuation,
- Reason for study discontinuation (eg, voluntary withdrawal, definitive pump explantation, death, lost to follow-up).

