All AEs will be followed until resolution or until the end of the follow-up period, whichever comes first.

Data Sources

Investigators at each site will collect and provide pre-specified data on study participants at baseline and during follow-up visits. Data elements provided by investigators and staff will be collected from information routinely recorded in the medical record, or will be prospectively recorded for the purposes of the study. No visits or examinations, laboratory tests or procedures are mandated as part of this study.

Information required to validate Serious Adverse Events (SAEs) will be requested from investigators and medical facilities as needed by the medical monitors, which may include confirmation of diagnoses or conditions and relatedness of AEs by the treating investigators, medical records including laboratory test results and imaging procedure results, and death certificates.

Study Size

This is a descriptive study that is not testing a hypothesis. As such, a formal sample size calculation is not performed. It is planned to recruit all patients who are willing to participate, from all trained investigators in certified centers in all participating European countries, and without a minimum designated for any country or region. The projected study size will be approximately 260 patients. No new patient or a very limited number of newly implanted patients is expected.

Data Analysis

Eligible patients will be those who have signed an informed consent form (ICF) and have received at least one dose of Insuman Implantable 400 IU/mL

• Primary analysis

Since the primary objective is to monitor the important identified risks, the analysis will be descriptive and the multiplicity control will not be considered.

For the important identified risks including severe hypoglycaemia, hyperglycaemia due to underdelivery of insulin, pump pocket infections, skin erosion, and abnormal healing, the time to first event will be depicted by the Kaplan-Meier plot. The cumulative event rate and its 95% confidence interval (CI) will be presented yearly.

The cumulative risk over the entire study and the instantaneous risk expressed as the hazard function over time will be presented graphically according to the time expressed in years and using a kernel smoothing method. A horizontal line will represent the incidence rate calculated, as number of patients with one or more events divided by the number of patients treated.

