8 RESEARCH QUESTION AND OBJECTIVES

8.1 PRIMARY OBJECTIVE

The primary objective of the study is to better characterize some of the following important identified risks:

- Severe hypoglycaemia,
- Hyperglycaemia caused by insulin underdelivery due to pump jamming, pump dysfunction or catheter occlusion),
- Pump pocket infection,
- Abnormal healing (at the surgical incision site after device implantation),
- Skin erosion.

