11 MANAGEMENT AND REPORTING OF ADVERSE EVENTS/ADVERSE REACTIONS

All Adverse Events (AE) regardless of seriousness or relationship to Insuman Implantable, spanning from the signature of the informed consent form until the end of the study as defined by the protocol for each patient are to be collected by the investigator and reported to the MAH/MAH representative within expedited time frame.

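### Abnormal healing is a post-implantation risk, but it is estimated over all treated patients, who enter after surgery, so the risk will be understated and the listed data items cannot correct it

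*Protocol*

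**What the plan says.** Section 8.1 of the protocol lists among the primary risks "Abnormal healing (at the surgical incision site after device implantation"), and Section 9.3.1.3 likewise ties it to the implantation procedure. Section 9.7.1 treats it like the other four risks: "skin erosion, and abnormal wound healing, the time to first event will be depicted by the Kaplan-Meier methodology". The same section adds a horizontal line for the crude incidence, which is patients with at least one event over all patients treated. It states no time origin for the Kaplan-Meier curve.

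Four other places decide who is observed, and when:

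- Section 9.2.2.1 admits "Patients with type 1 diabetes treated with Insuman Implantable 400 IU/mL in the MIP at study entry", so implantation precedes entry for everyone.
- Section 9.6.2.3 says that for new patients "the study entry visit should be performed as far as possible at the first clinical visit after pump implantation".
- Section 11 collects adverse events "spanning from the signature of the informed consent form until the end of the study as defined by the protocol for each patient".
- The abstract (Section 4) says that "approximately 260 implanted patients will be followed in the study" and, under Study Size, "No new patient or a very limited number of newly implanted patients is expected".

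The items listed in Section 9.6.2.3 include the initial date of intraperitoneal treatment and the initial date of commercial Insuman Implantable. They do not include the date on which the current pump was implanted or the date of any replacement. The pump-related history at entry names ketoacidosis, hyperglycaemia and severe hypoglycaemia.

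**The concern.** A healing complication needs a fresh incision. Someone whose incision healed before consent can have this event on study only after another operation, usually a pump replacement. Counting that person as event-free lowers the estimate without adding information about the risk. In addition, the interval most likely to produce the event, from surgery to the first clinic visit, lies before adverse event collection starts.

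The study exists to characterise these risks better. A low whole-cohort percentage for abnormal healing could be taken for the risk that a patient faces after implantation, and would then reassure wrongly.

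**Working it through.** **No plan figure to reproduce.** The 260 is a count of patients already included. Section 9.5.1 says: "As such, a formal sample size calculation is not performed". The protocol gives no expected rate and no precision target, so what follows is an illustration.

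**Does the unstated time origin matter?** There are three possibilities:

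1. Clock from study entry: patients with healed incisions sit in the risk set, and the estimate is diluted.
2. Clock from implantation, everyone counted from time zero: patients are treated as at risk over a period when their events were not being recorded, and the estimate is again too low.
3. Clock from the procedure with delayed entry at consent: the risk set is right, but it needs the date of the current pump and of each replacement, which are not listed. The initial intraperitoneal date does not date the current pump in anyone whose pump has already been replaced.

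Under all three, the crude proportion still uses every treated patient, and events before consent are still missing.

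**Inputs from the protocol (Sections 4 and 5):** N = 260; pump life L = 7 years; pump supply ends June 2019; first patient entered April 2016; the 260 were counted at Amendment 2, February 2018.

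**Assumptions, not in the protocol:** pump age at entry is uniform on 0 to 7 years; pumps are replaced only at end of life; recent first implantations and early replacements are ignored; the risk per procedure is p = 5%.

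**Share with a replacement on study**, f = (time from entry to end of supply) / L:

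- All enter April 2016: 3.17 / 7 = 45%, about 118 of 260.
- All enter April 2017, near the middle: 2.17 / 7 = 31%, about 80 of 260.
- All enter February 2018: 1.33 / 7 = 19%, about 50 of 260.

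The first and last are extremes, so 19% to 45% brackets the case of mixed entry dates. The remaining 55% to 81% would have no replacement observed. If replacements continued to December 2019, f would be 3.67 / 7 = 52% and 1.83 / 7 = 26%.

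**Whole-cohort risk** = f × p, so the understatement is 1 / f:

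- f = 45%: 0.45 × 5% = 2.25%; 1 / 0.45 = 2.2 times too low.
- f = 31%: 0.31 × 5% = 1.55%; 1 / 0.31 = 3.2 times too low.
- f = 19%: 0.19 × 5% = 0.95%; 1 / 0.19 = 5.3 times too low.

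The ratio does not depend on p; it is the same at 2% or 10%.

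**Example with exact (Clopper-Pearson) intervals**, at f = 31% (0.31 × 260 = 81 patients; 5% of 81 is about 4 events):

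- Over all patients: 4/260 = 1.5% (95% CI 0.4% to 3.9%).
- Over patients with an observed operation: 4/81 = 4.9% (95% CI 1.4% to 12.2%).

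The planned figure is lower and also looks more precise than the data on this risk allow.

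**The case against.** The strongest reply is that this belongs in the SAP. Section 9.7 defers the full analysis and the effect of the reduced sample to an amended SAP. Time origin and risk sets are normal SAP content, and for rare events Section 9.7.1 promises patient-years specific to the event. That is fair as regards the curve. It does not answer the crude denominator, which the protocol fixes, nor the dates, because an SAP cannot use what the listed items do not collect.

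A second reply is that the purpose is descriptive, and risk among treated patients is a legitimate real-life measure. This stands as a reason to keep the planned figure, but not to let it be the only one for a procedure-linked risk.

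Third, Section 9.9 already names depletion of susceptibles and says that separate analysis of long-term and new users can address it. The remedy is weak here: hardly any new users are expected, and they too enter after surgery. Section 9.7 names only country as an example subpopulation, and the checklist in Annex 2 marks stratified analyses as not applicable.

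A reader might infer more than the protocol supports:

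- That the whole cohort is also largely not at risk of pump pocket infection. Section 9.3.1.2 attributes infection to refill punctures, catheter replacement and investigation procedures as well, so everyone with a pump stays at risk. Only the surgical component is diluted.
- That the curve is fixed to start at study entry. Section 9.7.1 does not say so.
- That entry history is limited to three metabolic events. The list is open-ended; healing problems, infection and erosion are simply not named.
- That nobody in the cohort is recently operated. Section 9.1 includes patients implanted more recently, and the expectation of almost no new patients looks forward from February 2018. The number who consented soon after surgery is unknown.

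**Conclusion.** The point holds for abnormal healing. As planned, its post-implantation risk will be understated, because the crude denominator includes patients with no operation under observation and because events before consent are not collected as incident events. The direction follows from the protocol's own text. The size does not: about 2.2 to 5.3 times is an illustration that rests on uniform pump age, replacement at end of life only, and no allowance for recent first implantations or early replacements, each of which would raise the share with an observed operation and reduce the dilution. For pump pocket infection the concern is confined to surgery-related cases. The planned Kaplan-Meier analysis need not be dropped; it needs a procedure-based estimate beside it.

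**What to change.** - Add to the items in Section 9.6.2.3 the date of the current pump's implantation and of each on-study pump replacement, catheter replacement and explantation.
- For abnormal healing, make the main estimate events per observed implantation or replacement procedure, with an exact 95% CI, on a clock that starts at the procedure with delayed entry at consent. Show the planned whole-cohort figure beside it.
- Report pump pocket infection overall and also by time since the last procedure.
- Name pocket infection, abnormal healing and skin erosion since the current implantation under the pump-related history at entry, and report them separately from incident events.
- State in Section 9.9 that peri-operative events before consent are not captured as incident events.

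The cost is a few dates per patient from existing records, an e-CRF update and matching SAP wording. Some entry will be retrospective, and the interval for abnormal healing will be wider because its denominator is smaller.
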